3. *Penn Alcohol/Drug Craving Scale (PACS)*¹². A modified version of the PACS will be used to assess both alcohol and drug craving. The PACS is a 5-item measure including questions about frequency, intensity, and duration of craving, and an overall rating of craving for the previous week. The PACS has demonstrated good psychometric properties in our prior studies, including internal consistency reliability ($\alpha=.87$) and criterion validity^{6,7}.

In addition to these three questionnaires, the weekly progress measure will also include items to assess mindfulness practice (days/times per day) and homework assignment completion, as well as items relating to pain intensity, distress intensity, willingness to experience pain, and engagement in valued activity¹³.

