1. STUDY OBJECTIVES

1.1 **Primary Study Aims:** Determine the feasibility of an integrated psychosocial treatment (ACT + MBRP) in veterans with chronic pain with evidence of opioid-related problems. Chronic pain patients ($n = 120$) who are receiving opioid therapy and who are identified as opioid misusing, abusing, or dependent will be recruited from the Albuquerque Veterans Administration (VA) Hospital. Participants will be randomized to receive standard care or standard care in addition to ACT+MBRP. **Hypothesis 1: Feasibility of recruitment:** Given the high prevalence of both chronic pain and opioid-related problems in VA populations, we hypothesize it will be possible to recruit our target sample size ($n = 120$) within a 15-18 month timeframe. **Hypothesis 2: Feasibility of retention:** Drop-out rates will be consistent with other trials of similar psychosocial interventions for chronic pain (i.e., < 20%^{5,21-23}).

1.2 **Secondary Study Aims:** To examine weekly progress on specific therapy targets (e.g., pain acceptance, self-compassion, opioid craving) in the interventions in order to identify potential mechanisms of change and to identify the choice of intermediate endpoints for a larger randomized clinical trial.

Hypothesis 1: Evidence of treatment mechanisms: The combined ACT+MBRP treatments will be associated with changes in treatment mechanisms specified within the therapeutic models and in a manner consistent with that of previous work on ACT and MBRP, in comparison with standard care.

Hypothesis 2: Selection of intermediate endpoints: Weekly progress measures will provide data indicating measures of treatment-specific mechanisms that are most sensitive to change. We hypothesize that acceptance of pain discomfort will be most sensitive to change in ACT and that reductions in reactivity to substance craving will be most sensitive to change in MBRP.

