4.2 Exclusion Criteria

With regard to exclusionary criteria, participants will not be eligible for study participation if they: (1) meet diagnostic criteria for current substance abuse/dependence on a drug other than opioids, (2) meet diagnostic criteria for a current or past DSM diagnosis of schizophrenia, delusional disorder, psychotic or dissociative disorders, (3) are currently prescribed medications for opioid addiction (e.g., Buprenorphine/Naloxone/Suboxone),, or (4) history of suicide attempts or inpatient hospitalization for risk of suicide in the past six month. In addition, we will screen for significant suicidal ideation (e.g., marked intent or established plan) using a self-report measure at the baseline, post-treatment, and follow-up assessments. If significant ideation exists, the study RA will contact the VA's Acute Psychiatric Clinic, which provides on-call and immediate consultation and liaison services for the VA. The service is often consulted when significant ideation is identified.

During the study period, participants may become ineligible and may be involuntarily removed. The conditions for removal are detailed in the Consent Form. These conditions are summarized as follows: (1) Individuals may be removed if the study team discerns a significant worsening of stress or mood symptoms as a result of study participation, (2) if an participant is incarcerated, they cannot attend treatment sessions and will be removed, (3) if an individual becomes pregnant, their primary care provider will wean them off of opioids (due to documented birth defect risk associated with opioid use) which will render the participant ineligible for the study as they will no longer be taking opioids, and (4) if the participant displays behaviors that are deemed overly disruptive to other participants in the treatment group.

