Analyses to Test Secondary Aim Hypotheses. The primary goal of Aim 2 is to identify potential mechanisms of change and intermediate endpoints for future randomized clinical trials comparing ACT+MBRP to standard care. We will accomplish this goal by examining initial level and changes in targeted mechanisms over time during the course of treatment, as well as the association between changes in targeted mechanisms during treatment and 6-month follow-up measures of clinical outcomes. Targeted mechanisms will include (1) pain acceptance (2) psychological flexibility, (3) experiential avoidance, (4) opioid craving, and (5) reactivity to pain and craving, and will be examined using latent growth curve models with fixed effects of treatment and random effects of time. These analyses will provide an estimate of the initial level of each targeted mechanism (i.e., intercept) and the change in the targeted mechanisms over time (slope). Clinical outcome measures will include pain interference, pain behavior, and opioid misuse and will be examined using mediation analyses within the context of latent growth curve modeling⁶⁴, as we have done in prior studies^{63,65}. Specifically, as shown in simplified form in Figure 2, we will examine whether initial level (intercept) or changes (slope) in the targeted mechanisms ("M" in figure 2) during treatment mediate the effect of treatment on 6-month clinical outcomes, controlling for baseline levels of the outcomes. These analyses will also provide a test of Aim 2 Hypothesis 2, which is to identify those measures that are most sensitive to change (measures with the largest slope). Identifying measures that are more sensitive to change will help us in identifying intermediate endpoints for a larger RCT. Validation of intermediate endpoints is challenging and it is often recommended that meta-analytic methods be used⁶⁶, but alternative methods have been developed that allow for the evaluation of endpoints in mental-health clinical trials⁶⁷.

Figure 2. Simplified mediation model (excludes residual terms and covariances)

models will be estimated using the product of coefficients method⁶⁸, which provides an estimate of the mediated effect by multiplying regression coefficients for the regression of the mediators (e.g., slope of targeted mechanism) on treatment condition (i.e., a-path or α) and for the regression of the clinical

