- 7. When I'm down and out, I remind myself that there are lots of other people in the world feeling like I am.
- 8. When times are really difficult, I tend to be tough on myself.
- 9. When something upsets me I try to keep my emotions in balance.
- 10. When I feel inadequate in some way, I try to remind myself that feelings of inadequacy are shared by most people.
- 11. I'm intolerant and impatient towards those aspects of my personality I don't like.
- 12. When I'm going through a very hard time, I give myself the caring and tenderness I need.
- 13. When I'm feeling down, I tend to feel like most other people are probably happier than I am.
- 14. When something painful happens I try to take a balanced view of the situation.
- 15. I try to see my failings as part of the human condition.
- 16. When I see aspects of myself that I don't like, I get down on myself.
- 17. When I fail at something important to me I try to keep things in perspective.
- 18. When I'm really struggling, I tend to feel like other people must be having an easier time of it.
- 19. I'm kind to myself when I'm experiencing suffering.
- 20. When something upsets me I get carried away with my feelings.
- 21. I can be a bit cold-hearted towards myself when I'm experiencing suffering.
- 22. When I'm feeling down I try to approach my feelings with curiosity and openness.
- 23. I'm tolerant of my own flaws and inadequacies.
- 24. When something painful happens I tend to blow the incident out of proportion.
- 25. When I fail at something that's important to me, I tend to feel alone in my failure.
- 26. I try to be understanding and patient towards those aspects of my personality I don't like.

PENN ALCOHOL CRAVING SCALE (Modified)

Circle the most appropriate number for each item.

1. How often have you thought about doing drugs or drinking or about how good that would make you feel during the past week?

Never, that is, 0 times during the past week.	= 0
Rarely, that is, 1 to 2 times during the past week.	= 1
Occasionally, that is, 3 to 4 during the past week.	= 2
Sometimes, that is, 5 to 10 times during the past week or 1 to 2 times a day.	= 3
Often, that is, 11 to 20 times during the past week or 2 to three times a day.	= 4
Most of the time, that is, 20 to 40 during the past week or 3 to 6 times a day.	= 5
Nearly all of the time, that is, more than 40 times during the past week or more than 6 times a day.	= 6

2. At its most severe point, how strong was your craving during the past week?

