None at all.	= 0
Slight, that is a very mild urge.	= 1
Mild urge.	= 2
Moderate urge.	= 3
Strong urge, but easily controlled.	= 4
Strong urge and difficult to control.	= 5
Strong urge and would have done drugs or drink alcohol if it were available.	= 6

3. How much time have you spent thinking about doing drugs or drinking or about how that would make you feel during the past week?

None at all	= 0
Less than 20 minutes.	= 1
21-45 minutes.	= 2
46-90 minutes.	= 3
90 minutes-3 hours.	= 4
Between 3 to 6 hours.	= 5
More than 6 hours.	= 6

4. How difficult would it have been to resist doing drugs or drinking during **the past week** if you had known the drugs or alcohol were in your house?

Not difficult at all.	= 0
Very mildly difficult.	= 1
Mildly difficult.	= 2
Moderately difficult.	= 3
Very difficult.	= 4
Extremely difficult.	= 5
Would not be able to resist.	= 6

5. Keeping in mind your responses to the previous questions, please rate your overall average drug or alcohol craving for the **the past week**.

Never thought about drugs/drinking and never had the urge to do drugs/drink.	= 0
Rarely thought about drugs/drinking and rarely had the urge to do drugs/drink.	= 1
Occasionally thought about drinking and occasionally had the urge to do drugs/drink.	= 2
Sometimes thought about drinking and sometimes had the urge to do drugs/drink.	= 3
Often thought about drinking and often had the urge to do drugs/drink.	= 4
Thought about drugs/drinking most of the time and had the urge to do drugs/drink most of the time.	= 5
Thought about drugs/drinking nearly all of the time and had the urge to do drugs/drink nearly all the time.	= 6

Weekly Diary (pg 1)

Wk# _____

1.

Rate how bad your pain was overall in the past week.

None 0 1 2 3 4 5 6 7 8 9 10 Worst Possible

2.

Rate how upset and/or distressed you were overall in the past week.

None 0 1 2 3 4 5 6 7 8 9 10 Worst Possible

3.

Rate how willing were you to have pain and distress in the past week.

Not Willing at All 0 1 2 3 4 5 6 7 8 9 10 Most Willing

4.

Rate how much effort you put in to making pain or upsetting thoughts, feelings, or memories go away this past week.

None 0 1 2 3 4 5 6 7 8 9 10 Most Effort

5.

Rate how effective you were in taking actions that contributed to a better, more vital, quality of living in the past week.

Not at all 0 1 2 3 4 5 6 7 8 9 10 Most Effective

6.

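### The mechanism called opioid craving is scored from a pooled alcohol-and-drug scale that never names opioids, and the three middle options of its summary item drop drugs from the thought clause

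*Combined protocol and SAP*

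**What the plan says.** Section 1.2 sets out to track weekly "specific therapy targets (e.g., pain acceptance, self-compassion, opioid craving" and to use the results to choose intermediate endpoints for a larger trial. Section 9.1 lists the mechanisms to be modelled as growth curves and tested as mediators, among them "3) experiential avoidance, (4) opioid craving, and (5) reactivity to pain and craving".

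The instrument given for craving, in the synopsis and in section 6.2.4, is a five-item scale: "A modified version of the PACS will be used to assess both alcohol and drug craving". Section 6.2.5 and the description of research material in section 7 also call what it measures alcohol and drug craving.

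The form is printed in Appendix IV. Item 1 begins "How often have you thought about doing drugs or drinking". Option 2 of the summary item, item 5, reads "Occasionally thought about drinking and occasionally had the urge to do drugs/drink".

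Participants use prescribed opioids daily for at least 90 consecutive days (section 4.1). Section 4.2 excludes those who "meet diagnostic criteria for current substance abuse/dependence on a drug other than opioids".

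**The concern.** The plan uses two names for one score. The aim and the model call it opioid craving; the measurement sections call it alcohol and drug craving, and the printed form matches the second name. A veteran taking opioids as prescribed may or may not count that as doing drugs, and any craving for alcohol adds to the same score.

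The summary item has a further fault that does not depend on how participants read the word drugs: its middle options are worded differently from those at either end.

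What is at stake is interpretation. The four MBRP sessions are directed at opioid triggers, urges and craving, and the weekly slopes are meant to show which measures deserve to be endpoints next time. If the craving score is partly off target, a flat slope or a null mediated effect could be reported as no change in opioid craving, or craving could be dropped as a candidate endpoint for the wrong reason.

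**Working it through.** The plan gives no figure to reproduce here, so the check sets the construct against the form item by item.

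**1. Construct named**

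| Place | Name used |
|---|---|
| Synopsis objectives; section 1.2 aim; section 2.2 rationale | opioid craving |
| Section 9.1, mechanism 4 | opioid craving |
| Section 1.2, Hypothesis 2 | reactivity to substance craving |
| Synopsis and section 6.2.4, description of the measure | alcohol and drug craving |
| Sections 6.2.5 and 7 | alcohol/drug craving |

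**2. Substance named in each item (Appendix IV)**

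| Item | Substance |
|---|---|
| 1 | drugs or drinking |
| 2 | none in the stem; the top option names drugs or alcohol |
| 3 | drugs or drinking |
| 4 | drugs or drinking |
| 5 | drug or alcohol craving |

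Items naming opioids or pain medication: 0 of 5. Stems pooling drugs with alcohol: 4 of 5 (items 1, 3, 4 and 5).

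**3. Item 5, option by option**

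| Score | Thought clause | Urge clause |
|---|---|---|
| 0, 1 | drugs/drinking | drugs/drink |
| 2, 3, 4 | drinking only | drugs/drink |
| 5, 6 | drugs/drinking | drugs/drink |

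Three of the seven options, the middle of the 0 to 6 range, have a thought clause limited to drinking. A non-drinker who sometimes thinks about drugs and sometimes has the urge finds the urge half of option 3 true and the thought half untrue. The same holds for options 2 and 4.

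**4. How much of the score the item 5 fault touches**

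The documents state no scoring rule. If the five items are summed with equal weight (an assumption), the maximum is 5 × 6 = 30 and item 5 supplies 6 / 30 = 20% of it. The inconsistent options are then confined to one fifth of the score range; the pooled wording affects the rest as well.

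**5. Whether another weekly measure fills the gap**

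- The weekly diary ratings cover pain, distress, willingness, effort to control, and effective action. None concerns craving. The printed numbering jumps from 6 to 9, but the synopsis list of additional weekly items includes none on craving.
- Item 6 of the Current Opioid Misuse Measure (COMM) asks about time spent thinking about opioid medications. It belongs to a misuse scale with a 30-day recall, which is not among the weekly measures and so cannot supply the weekly slope.

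The modified PACS is therefore the only source for the mechanism that section 9.1 calls opioid craving.

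**The case against.** The strongest reply is that the plan is open about the pooling: several sections say the scale covers alcohol and drugs. With current dependence on other drugs excluded, the word drugs may well point participants towards opioids. Hypothesis 2 is worded "reductions in reactivity to substance craving will be most sensitive to change in MBRP", which a pooled scale fits better than an opioid-only one would. The item 5 wording looks like an editing slip in one item of five, the options are numbered and ordered, and the urge clause still mentions drugs. All this concerns one of five mechanisms in a secondary aim of a feasibility trial.

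Much of that stands, and it limits the point. It does not remove the mismatch between "4) opioid craving" in the model and the printed form, and it does not justify leaving the middle options out of line.

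A reader might go further in several ways that the documents do not support:

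- **A loss of power of stated size.** This would need a correlation between the pooled score and opioid craving, and none is given. A single two-group comparison is also not the planned analysis, which is growth-curve slopes with a bootstrapped mediated effect. One study cited in section 6.2.4 for the scale's performance is also among the sources of the MBRP effect sizes in section 9.2, so those effects may already reflect measurement with this scale.
- **Loss of the cited validation.** The reliability of .87 is credited to the team's prior studies, and the documents do not say whether those used this modified wording.
- **A floor effect.** It is plausible, but nothing in the documents shows it.
- **Middle options that omit drugs altogether.** They do so only in the thought clause.

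**Conclusion.** The concern holds in two parts. First, the aim and the model name opioid craving, but the only weekly craving score pools alcohol and drugs and names opioids in 0 of 5 items. Second, 3 of the 7 options of item 5 are inconsistent with the other 4 in the thought clause. The second is a plain wording error. The first is a mismatch between label and measure that can be settled either by changing the label or by adding to the measure.

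The consequence is a score that may misstate opioid craving and a null that could be misread. Its direction and size cannot be derived from the documents: how participants read the word drugs, and how much alcohol craving they have, are both unknown. Recruitment and retention, the primary outcomes, are unaffected.

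**What to change.** 1. In item 5, put drugs and drinking together in the thought clause of options 2, 3 and 4, so that all seven options are parallel.
2. Then choose one of two routes.
   - *Relabel:* call the PACS score alcohol/drug craving in the aim, the list of mechanisms in section 9.1 and the conclusions.
   - *Add:* if opioid craving is the intended mechanism, include a short opioid-specific craving item in the weekly set and score it separately. Word it to ask about craving or urges beyond taking the medication as prescribed. Keep the pooled PACS for comparability.
3. If the scale itself is reworded instead, include the top option of item 2, which also names drugs and alcohol. Simply substituting opioid pain medication for drugs or drinking would be a poor exchange: in people who take prescribed opioids daily, items 1 and 3 could then count thoughts about ordinary dosing as craving, and item 4 would ask about resisting medication they are prescribed. Full rewording is thus a trade-off, whereas steps 1 and 2 are straightforward corrections.

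The cost is one questionnaire revision through the IRB and slightly less comparability with earlier PACS studies. The second route also adds a little weekly response time.

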Appendix V

Study Completion/Termination

Pilot Study of Combined Treatment for Veterans with Chronic Pain and Opioid Misuse

Pt_ID: _____ Visit Date: ____ / ____ / ____

1. Date of final study visit: / /
d d m m m y y y y
2. Stage at which participant ended participation:

3. Primary reason for terminating participation in the study:
 Completed study
 Participant was determined after enrollment to be ineligible (provide comments):

 Participant withdrew consent
 In the principal investigator's opinion, it was not in the participant's best interest to continue (provide comments):

 Adverse event (If checked, complete the AE form.)
 Death
 Lost to follow-up
 Other (specify):

 Unknown

Comments:

PI Signature: _____ Date: _____

Appendix VI
Participant Remuneration Log

Pilot Study of Combined Treatment for Veterans with Chronic Pain and Opioid Misuse

Pt_ID: _____

1. \$60 for completion of the baseline session Yes No

Date of payment: / / d d m m m y y y y

2. \$5 per week for completing weekly assessments during active treatment:

WEEK	DATE PAID
1 – ACT	
2 – ACT	
3 – ACT	
4 – ACT	
5 – ACT	
6 – ACT	
7 – ACT	
8 – ACT	
9 – MBSR	
10 – MBSR	
11 – MBSR	
12 – MBSR	

3. \$50 for completing the end of treatment assessment (week 13): Yes No

Date of payment: / / d d m m m y y y y

4. \$50 for completing the six-month follow-up (week 37): Yes No

Date of payment: / / d d m m m y y y y

5. Did participant complete all assessments? Yes No

If **yes**, provide \$50 bonus payment at the 6-month follow-up.

Date of payment: / / d d m m m y y y y

Total Remuneration to Participant (*upon completion or termination*): \$ _____

Comments (e.g. note here if participant terminates prior to receiving full compensation):

Appendix VIII
Protocol Deviation Tracking Log

Protocol ID/Number:				Site Name/Number:		VA Medical Center, Albuquerque, NM		
Protocol Title (Abbreviated):		Combined Treatment for Chronic Pain and Opioid Misuse						
Principal Investigator:					Page number [1]:			
Ref No.	Subject ID	Date of Deviation	Date Identified	Deviation Description	Dev. Type [2]	Resulted in AE?	Did Subject Continue in Study?	Meets IRB Reporting Req. (Yes/No)
1								
2								
3								
4								
5								
6								
7								

Investigator Signature: _____

Date: _____

Form Instructions:

- [1] Each page should be separately numbered to allow cross-referencing (e.g., deviation #2 on p. 7)
- [2] Deviation Type: (A-J) See codes below—enter the appropriate deviation code from the list.

Protocol Deviation Codes:

- A – Consent Procedures
- B – Inclusion/Exclusion Criteria
- C – Concomitant Medication/Therapy
- D – Laboratory Assessments/Procedures
- E – Study Procedures
- F – Serious Adverse Event Reporting/Unanticipated Adverse Device Effect
- G – Randomization Procedures/Study Drug Dosing
- H – Visit Schedule/Interval
- I – Efficacy Ratings
- J – Other

Adverse Event Form

Pilot Study of Combined Treatment for Veterans with Chronic Pain and Opioid Misuse

Pt_ID: _____	This form is cumulative and captures adverse events of a single participant throughout the study.
--------------	--

Severity	Study Event Relationship	Action Taken Regarding Study Intervention	Outcome of AE	Expected	Serious Adverse Event (SAE)
1 = Mild 2 = Moderate 3 = Severe 4 = Life-Threatening	0 = Not related 1 = Unlikely related 2 = Possibly related 3 = Probably related 4 = Definitely related	0 = None 1 = Dose modification 2 = Medical Intervention 3 = Hospitalization 4 = Intervention discontinued 5 = Other	1 = Resolved 2 = Recovered with minor sequelae 3 = Recovered with major sequelae 4 = Ongoing/Continuing treatment 5 = Condition worsening 6 = Death 7 = Unknown	1 = Yes 2 = No	1 = Yes 2 = No (if yes, complete SAE form)

At end of study only: Check this box if participant had no adverse events None

**Serious Adverse Event (SAE)
Report Form**

Pilot Study of Combined Treatment for Veterans with Chronic Pain and Opioid Misuse

Pt ID: _____	Date Participant Reported: _____/_____/_____ d d m m m y y y y
---------------------	---

1. SAE onset date: ____/____/_____
d d m m m y y y

2. SAE stop date: ____/____/_____
d d m m m y y y

3. Location of SAE: _____

4. Was this an unexpected adverse event? Yes No

5. Brief description of participants with no personal identifiers:

Sex: F M Age: _____

Diagnosis for study participation: _____

6. Brief description of the nature of the SAE (attach description if more space is needed):

7. Category of the SAE:

Date of death ____/____/
(dd/mmm/yyyy)

Congenital anomaly/birth defect

Life threatening

Required intervention to prevent permanent
impairment

Hospitalization – initial or prolonged

Other: _____

Disability/incapacity

8. Intervention type:

Behavioral/lifestyle (specify): Psychosocial intervention: Combined ACT and MBSR

9. Relationship of event to intervention:

- Unrelated (clearly not related to the intervention)
- Possible (may be related to intervention)
- Definite (clearly related to intervention)

10. Was study intervention discontinued due to event? Yes No

11. What medications or other steps were taken to treat the SAE?

12. List any relevant tests, laboratory data, and history, including preexisting medical conditions:

13. Type of report:

- Initial
- Follow-up
- Final

Signature of principal investigator: _____ Date: _____

